1.3 Schema

The general study design is summarised in Figure 1.

ACEi angiotensin converting enzyme inhibitor; ARB angiotensin receptor blocker; CKD chronic kidney disease; eGFR estimated glomerular filtration rate; EP endpoint; MRI magnetic resonance imaging; PK pharmacokinetic; sUA serum uric acid; UACR urinary albumin to creatinine ratio

2 INTRODUCTION

Chronic kidney disease is a major public health problem, and its global burden is expected to further grow due to an aging population. Currently CKD management focuses on blood pressure, glycaemic control, and treatment with an ACEi or ARB. Although it is well accepted that hyperuricaemia is associated with CKD, the effects of UA-lowering therapy in patients with CKD remain uncertain.

Uric acid is a purine metabolite generated by the liver during turnover of nucleic acids. It is primarily excreted by the kidneys (two thirds) as well as the gastrointestinal tract (one third) (reviewed by Hyndman et al 2016). Numerous cross-sectional and epidemiological studies have shown the association of sUA level concentrations and CKD in both the general population and in patients with CKD (Mohandas and Johnson 2008). The harmful effects of sUA on kidneys are ascribed to direct cytotoxicity including the proximal tubule of the kidney due to its accumulation (and crystallisation) within cells, and activation and upregulation of inflammation by sUA (Mohandas and Johnson 2008).

UA-lowering therapy may prevent progression of CKD but the conclusion is very uncertain. Larger well-designed studies are required to study the effect of UA-lowering therapy on CKD progression.

2.1 Study rationale

Evidence shows independent associations between hyperuricaemia and the risk of hypertension, myocardial infarction, CKD, type 2 diabetes, heart failure, and metabolic syndrome, including obesity (Nakagawa et al 2006, Grayson et al 2011, Kodama et al 2009, Leyva et al 1998, Anker et al 2003). Furthermore, gout, an inflammatory arthritis caused by deposition of monosodium urate crystals in joints, is associated with an increased risk of all-cause death, as well as CV death (Iochimescu et al 2008, Kim et al 2008, Niizeki et al 2006, Jankowska et al 2007). Hyperuricaemia (elevated levels of urate in the circulation) is a prerequisite for development of gout, an inflammatory arthritis caused by deposition of monosodium urate crystals in joints. Gout occurs in patients with serum urate >6.8 mg/dL, which is the solubility limit of monosodium urate. The prevalence of gout increases with higher serum urate (Choi et al 2005). However, the causal relationship between hyperuricaemia / gout and the aforementioned diseases and outcomes remains to be proven.

URAT1 is responsible for reabsorption of UA in the proximal tubule. Inhibition of URAT1 results in increased urinary excretion of UA. Verinurad is a novel URAT1 inhibitor in Phase 2 development for CKD and heart failure. Verinurad combined with the XOIs febuxostat or allopurinol has been shown to lower sUA in patients with recurrent gout in Phase 2 studies by up to 80% (see Investigator's Brochure, Section 5.2.2.3 through Section 5.2.2.5 for details on Studies 204, 205, and 206). The extensive lowering of sUA delivered

presents a unique opportunity to explore whether intensive urate lowering therapy can improve kidney function and/or cardiac health. Currently no sUA-reducing drug is approved to treat CKD, thus presenting a potential to target a novel therapeutic pathway.

Potent URAT1 inhibition has been associated with creatinine elevation in some patients, potentially related to increased sUA peak concentrations of uUA in the proximal tubuli of the kidney. Verinurad is therefore given as an extended release formulation as a low maximum concentration is expected to further reduce or eliminate the risk of creatinine elevations. Moreover, verinurad is to be developed exclusively in a fixed-dose combination with an XOI, reducing also the production of UA.

The Phase 2a study D5495C00007 was performed using 9 mg verinurad given as the ER8 capsule and 80 mg febuxostat administered once daily in combination for 24 weeks. The primary endpoint was UACR at 12 weeks.

Sixty patients were randomised. At enrolment, the treatment arms in study D5495C00007 were generally balanced with regards to common clinical parameters.

The study met the primary endpoint at 12 weeks. UACR was significantly reduced by 39.4% for patients randomised to be treated with verinural and febuxostat compared to placebo (p=0.0747). The comparison between the active arm and the control arm indicated statistical significance was achieved, considering the predetermined alpha (0.1). The effect on UACR was rapid, with full effect achieved at the first on-treatment assessment time point at 1 week, and did not appear to be driven by outliers. The therapeutic effect persisted with an LS mean of percent change from baseline in UACR compared to placebo (90% CI) -49.26 (-68.206, -19.009) at Week 24.

Mean baseline eGFR in the trial was 59 and 68 mL/min/ 1.73 m^2 in the active and control arms, respectively. There were no changes in eGFR in either arm, either at the early or late assessment time points. However, considering the limited sample size, eGFR variability, and short duration of treatment, this is not unexpected. Overall the treatment was well tolerated and safety findings in the study were consistent with the known safety profile of the drug.

The overall clinical evidence suggests that the combination of verinurad and XOI has clinical benefit and an acceptable safety profile in CKD patients and that further development is warranted. Hence, a global, randomised, Phase 2b study is planned to evaluate the efficacy and safety of verinurad and allopurinol in patients with CKD and hyperuricaemia.

2.2 Background

Verinurad is a novel URAT1 inhibitor in Phase 2 development. Verinurad combined with the XOI febuxostat has been shown to lower UACR in patients with diabetes and albuminuria,

and to lower sUA by >80% in patients with recurrent gout in Phase 2 studies. Please refer to the Investigator's Brochure for full details on safety and efficacy of verinurad.

2.2.1 Verinurad in combination with allopurinol

Study RDEA3170-206 was a Phase 2a, randomised, open-label, multicentre study to assess the pharmacokinetics (PK), pharmacodynamics (PD), and safety of verinurad administered in combination with allopurinol (300 mg qd) compared with allopurinol administered alone (300 mg once daily, 300 mg twice daily, or 600 mg once daily) in adult patients with gout. There were 40 male patients and 1 female patient randomised into the study. sUA was decreased in a dose-dependent manner in patients treated with multiple once daily doses of verinurad ranging from 2.5 to 20 mg given as the MR4 tablet in combination with allopurinol 300 mg. All verinurad and allopurinol 300 mg combination treatments resulted in greater reductions in sUA compared with allopurinol 300 mg dosed alone.

2.3 Benefit/risk assessment

More detailed information about the known and expected benefits and risks and reasonably expected adverse events (AEs) of verinurad and allopurinol may be found in the Investigator's Brochure.

The study design aims to minimise potential risks to patients and to ensure adequate monitoring. A dual-inhibition approach using lower doses of 2 agents with complementary mechanisms of action is expected to synergistically improve efficacy outcomes while reducing potential safety issues that would be of concern with higher doses of each agent alone.

The main toxicity of concern noted with verinurad monotherapy is creatinine elevations >1.5x baseline occurring in 6.2% of Caucasian patients in Study RDEA3170-201, and in 17.1% of Japanese patients in Study RDEA3170-203. When verinurad was combined with XOI in Studies RDEA3170-204, RDEA3170-205 and RDEA3170-206, no creatinine elevations were reported. In the current study, verinurad will therefore exclusively be administered in combination with allopurinol. In the CKD Phase 2a study D5495C00007, in which a similar patient population was recruited as in this study, the combination of verinurad and febuxostat resulted in the same rate of creatinine elevations in both the active treatment group and in the placebo control group.

In previous studies, verinural combined with allopurinol was well tolerated and associated with acceptable side effects. Most AEs were minor and not related to treatment.

CKD with hyperuricaemia represents a significant unmet medical need and underlines the need for novel therapies for this patient population. Verinurad combined with allopurinol may demonstrate a meaningful clinical benefit and an acceptable safety profile. The overall

benefit-risk profile of verinurad combined with allopurinol is expected to be favourable, therefore supporting the current study design.

Patients with CKD are at increased risk to experience CV events, and several studies showed that both reduced renal function and proteinuria are associated with such events. Furthermore, CV events have been identified as a risk for lesinurad, which is an approved drug with a similar mechanism of action as verinurad. Few CV events were reported in the verinurad clinical programme. Important actions aiming to minimise the CV risk to patients in this study include using allopurinol instead of febuxostat, as allopurinol treatment is associated with a lower risk of CV death (White et al 2018). Also, high-risk patients such as patients with recent CV events or inadequate blood pressure control will be excluded.

The main risk from allopurinol, skin reaction, will be minimised by excluding patients carrying the high risk Human Leukocyte Antigen-B (HLA-B) *58:01 allele and administration of allopurinol via a slow dose titration.

Patients with gout may experience an acute gout flare event with initiation or an increase in dose of urate-lowering therapies (Borstad et al 2004). To prevent this, the manufacturer's prescribing information for urate-lowering therapies like lesinurad, allopurinol and febuxostat, as well as the European League Against Rheumatism (EULAR), American College of Rheumatology (ACR), and British Society of Rheumatology treatment guidelines Zhang et al 2006; Jordan et al 2007; Khanna et al 2012), recommend acute gout flare prophylaxis with colchicine, steroids, or a NSAID when initiating or increasing the dose of such therapies. The protocol lists options for gout prophylaxis to the investigators to allow for appropriate management (Section 6.5.1).

Following a blinded interim analysis in September 2020, the study was modified (via Protocol Version 5.0) to explore a broader range of doses, and a 24 mg dose of verinurad will be introduced to a subset of patients in the 3 mg cohort. This subset will consist of patients randomized to 3 mg verinurad who have a planned Visit 9 after Protocol Version 5.0 is implemented in the respective territories and once IP is available.

Testing a higher dose of verinurad requires careful consideration. Based on the safety information from the blinded interim analysis, as well as the evidence accumulated throughout the verinurad clinical development program, there are no major concerns precluding testing 24 mg verinurad with regards to safety. Verinurad has previously been administered to healthy subjects for 7 days using the same formulation (ER8) at 12 and 24 mg in the JADE study (D5495C00006) without safety concerns (refer to Investigator's Brochure).

In the new dosing regimen, all subjects will end treatment at Visit 10, therefore no patients will be treated with 24 mg verinurad for longer than approximately 13 weeks.

Overall, the study has been designed to minimise the risks to participating patients by excluding patients at high risk of AEs and by applying appropriate safety monitoring of recruited study patients. The doses selected have been carefully considered in light of the target patient population. The potential benefits of developing a new treatment for CKD with hyperuricaemia therefore outweigh the limited risks to the patients exposed to treatment with verinurad and allopurinol in this trial.

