For the new dosing regimen, following Protocol Version 5.0 implementation, patients will be instructed thoroughly and receive new dosing card instructions at Visit 9. They will be instructed to take 1 tablet daily from one bottle of allopurinol/matching placebo and 1 capsule daily from each of two verinurad/matching placebo bottles that will be differentiated by the label colour.

- ^b Only performed at Week 60 visit if this visit occurs before Protocol Version 5.0 implementation.
- c Vital signs include temperature, pulse rate, blood pressure measurement.
- ^d Serious adverse events will be collected from the time of signature of informed consent form at Visit 2, throughout the treatment period and including the follow-up period and last contact. Adverse events will be collected from the time of the first dose of IP. Changes in medical history between the time of signature of the informed consent form and the first dose of IP will be reported as medical history.
- For women of childbearing potential, pregnancy urine dipstick tests will be conducted on site. A serum pregnancy test will be done by central laboratory after 2 positive urine tests.
- ^f Mandatory HLA-B*5801 allele testing prior to randomisation for all patients. Patients known to be positive for HLA-B*5801 cannot be randomised.

g CC

- ^h Verinurad, allopurinol and oxypurinol (active metabolite of allopurinol) plasma concentrations will be assayed.
- ⁱ Study medication should be dispensed at end of visit
- ^j At Visit 5 (approximately 8 weeks after randomisation) through Visit 9, titration to step-3 target dose will only be allowed if the patient's eGFR was ≥30 mL/min/1.73m² at Visits 3 and 4.

Table 2Schedule of activities – Extension treatment, end of treatment, and follow-up period (Visits 11 through 14
applicable only to patients who passed Week 60 prior to Protocol Version 5.0 implementation)

Visit	For all patients: End of treatment (EOT)/early discontinuation ^a	For all patients: Follow up visit (4 weeks after EOT/early	Details in CSP section or				
	11	12	13	14		discontinuation/ last scheduled, numbered visit ^b)	Appendix
Week	72	84	96	108			
Window	±7d	±7d	±7d	±7d		±7d	
Full physical examination					X	Х	Section 8.2.2
Brief physical examination	Х			х			Section 8.2.2
Vital signs °	х	х	х	Х	x	х	Section 8.2.3
Weight	х	х	х	Х	x	х	Section 8.2.2
ECG					X	х	Section 8.2.4
Concomitant medication	Х	Х	Х	Х	X	х	Section 6.5
Adverse events ^d	Х	х	х	Х	X	Х	Section 8.3

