4.1.2.9 Week 47 (Visit 9)

At the time of implementation of Protocol Version 5.0, a new dosing regimen will be introduced to assess the higher dose of 24 mg verinurad. Patients in the 3 mg verinurad cohort

who will have Visit 9 planned after the amendment implementation in the respective country/site and who have signed ICF for the new dosing regimen will be switched to 24 mg dose at Visit 9. Patients who do not consent should be discontinued from the study at a subsequent visit.

To introduce the new 24 mg dose, a new dosing regimen will be initiated across treatment arms to maintain blinding. For verinurad dosing, all patients in the new dosing regimen will receive 2 capsules through addition of a matching placebo capsule, with the exception of those who switched from the 3 mg to 24 mg dose, where two 12-mg verinurad capsules will be given. Allopurinol dosing will remain the same.

Note: Patients will only be allowed to switch to the new dosing regimen's treatments introduced under Protocol Version 5.0 if the patient's eGFR was \geq 30 mL/min/1.73m² at Visit 8. Management of patients with eGFR <30 mL/min/1.73m² at Visit 9 should be discussed with the medical monitor.

- Place phone calls on the day before the visit to remind patients to record the time and date of the study medication intake on the day of the visit
- Collect first morning void samples from 3 days before visit
- Collect untaken study medication
- Update concomitant medication
- Record AEs
- Record vital signs
- Record weight
- Obtain blood samples for post-dose PK and sUA (drug taken at home, date and time of drug intake should be recorded)
- Obtain blood samples for efficacy assessments (s-UA, creatinine, eGFR, Cystatin C, NTproBNP)
- Perform pregnancy urine dipstick test for women of childbearing potential; after 2 positive urine tests, a serum pregnancy test is to be done by central laboratory
- Prior to Protocol Version 5.0, IVRS/IWRS and dispense titration Step-3 dose (Note: Titration to step-3 target dose will only be allowed if the patient's eGFR was ≥30 mL/min/1.73m² at Visits 3 and 4.)
- Dispense containers for morning voids

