F 2.1 Patients with baseline eGFR \geq 40 mL/min/1.73 m²

F 2.1.1 Serum creatinine increase to \geq 1.5-fold from baseline

- Assess the patient to identify and manage any potential contributing factor. Correct any dehydration and ensure the patient is well hydrated prior to next renal safety monitoring visit.
- At the investigator's discretion, the patient may continue with study treatment, and retest of serum creatinine should be performed the following week. If the underlying cause (eg, dehydration) is still present at the next evaluation, the investigator should carefully consider if the retesting should be postponed for another week.
- Patient should attend the following week for repeat serum creatinine measurement. If an underlying potentially treatable cause (eg, dehydration) is still present, the investigator should treat this appropriately and postpone testing for up to a week.
- Subsequent management will depend on the repeat measurement(s):
 - If serum creatinine <1.5-fold of baseline value for two successive measurements, the patient may restart/continue with study treatment and the original study visit schedule.
 - If repeat serum creatinine is between ≥1.5 to <2.0-fold of baseline value, the patient should be evaluated every 1 to 2 weeks. During this evaluation period, the randomised treatment can be temporarily interrupted at the investigator's discretion. If serum creatinine is <1.5-fold of baseline value during the evaluation period, study treatment may be restarted/continued on the original study visit schedule.
 - If serum creatinine ≥2.0-fold of baseline value for 2 successive measurements (including the original high value if applicable), randomised treatment should be permanently discontinued and the patient should be followed up as per study schedule.

F 2.2 Patients with baseline eGFR <40 mL/min/1.73 m²

The CKD-EPI formula (Michels et al 2010) should be used to estimate GFR for enrolment criteria, baseline value and subsequent on-study measurements.

More intense renal monitoring and discontinuation are based on % drop from the baseline value.

F 2.2.1 If eGFR drops to <75% of the baseline value

- Assess the patient to identify and manage any potential contributing factor. Correct any dehydration and ensure the patient is well hydrated prior any future evaluation.

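### No creatinine is scheduled between the switch to 24 mg verinurad (Week 47) and end of treatment (Week 60), so the renal rules can reach 24 mg only through unscheduled tests; the last safety panel and ECG before the switch date from Week 34

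*Supplement*

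**What the plan says.** - **The switch.** Sections 4.1.1, 4.1.2.9 and 6.1.1 move eligible patients in the 3 mg arm to 24 mg at Visit 9 (Week 47), with allopurinol unchanged. Section 2.3 adds that "all subjects will end treatment at Visit 10, therefore no patients will be treated with 24 mg verinurad for longer than approximately 13 weeks". Its closing paragraph rests the benefit-risk case partly on the monitoring of recruited patients.
- **The toxicity.** Section 2.3 states: "The main toxicity of concern noted with verinurad monotherapy is creatinine elevations >1.5x baseline". It adds: "When verinurad was combined with XOI in Studies RDEA3170-204, RDEA3170-205 and RDEA3170-206, no creatinine elevations were reported". It also reports that elevations were equally frequent on active treatment and placebo in the Phase 2a CKD study. Section 8.3.9 makes clinically significant acute creatinine changes an event of special interest.
- **Visit 9 procedures.** Section 4.1.2.9 lists "Obtain blood samples for efficacy assessments (s-UA, creatinine, eGFR, Cystatin C, NTproBNP". Table 1 leaves the safety laboratory row (chemistry, haematology, urinalysis) and the ECG row blank at Visit 9. Both are marked at Visits 8 and 10.
- **Dispensing.** A Table 1 footnote says "Study medication should be dispensed at end of visit".
- **Renal rules.** Appendix F 2.1.1 (baseline eGFR of 40 or more) starts from a measured creatinine rise to 1.5-fold. If the patient stays on treatment, "retest of serum creatinine should be performed the following week". It then provides for repeat evaluation with possible interruption, and for permanent discontinuation after two successive values of at least 2.0-fold. Appendix F 2.2.1 follows the same pattern on eGFR for patients with lower baseline values.
- **eGFR gate.** The switch requires an eGFR of at least 30 at Visit 8. An eGFR below 30 at Visit 9 is to be discussed with the medical monitor.

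**The concern.** Appendix F 2 is a sequence: detect, retest, pause, stop. It needs a measured value while the patient is still taking the drug. For 24 mg, the first scheduled measurement falls at the visit where treatment ends, so the sequence has no scheduled starting point during the exposure it is meant to protect. The cited experience with 24 mg of this formulation is 7 days in healthy subjects (Section 2.3), so these 13 weeks are the first longer exposure that the protocol describes.

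There is also a reference problem for the other safety measures. Liver and other chemistry, haematology, dipstick and ECG have no value at the switch. A change between Weeks 34 and 60 cannot be assigned to 24 mg alone.

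**Working it through.** **1. Length of exposure.** Table 1 places Visit 9 at Week 47 and Visit 10 at Week 60, each ±7 days.
- Nominal: 60 − 47 = 13 weeks, which reproduces the Section 2.3 figure.
- Shortest: (420 − 7) − (329 + 7) = 77 days = 11 weeks.
- Longest: (420 + 7) − (329 − 7) = 105 days = 15 weeks.
- The synopsis gives about 12 weeks after Visit 9, a small discrepancy.

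**2. Scheduled measurements around the switch** (Table 1; Sections 4.1.2.8 to 4.1.2.12).

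| Measure | Last before 24 mg | Between Weeks 47 and 60 | First after switch |
|---|---|---|---|
| Creatinine, eGFR, cystatin C, sUA | Week 47 | 0 | Week 60 |
| Other safety chemistry, haematology, dipstick | Week 34 | 0 | Week 60 |
| ECG | Week 34 | 0 | Week 60 |

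The Visit 9 blood values precede 24 mg because drug is dispensed at the end of the visit. For the second and third rows the gap is 60 − 34 = 26 weeks, of which 47 − 34 = 13 are on 3 mg and 13 on 24 mg.

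**3. Comparison with the initial titration.** Steps 1, 2 and 3 are dispensed at Weeks 0, 4 and 8, and creatinine is drawn at Weeks 4, 8 and 12, so 4 weeks after each step. In the high-dose arm the verinurad steps are 7.5/3 = 2.5-fold and 12/7.5 = 1.6-fold. The Visit 9 step is 24/3 = 8-fold.

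**4. Can Appendix F 2 operate on schedule?** It needs a first raised value and a retest about a week later, with treatment still running. Scheduled values on 24 mg before the stop visit number zero. A raised Week 60 value can be followed up, but it can no longer change 24 mg dosing.

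**5. The eGFR wording.** The gating value (Visit 8) is 13 weeks old at the switch. For step 3, dispensed at Visit 5, the more recent gating value (Visit 4) is 4 weeks old. The Visit 9 eGFR comes from blood drawn at the visit that ends with dispensing. No laboratory turnaround is given, so the text does not show how a result below 30 would be known before the new kit is handed over.

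**6. Number of patients.** Assume that 36 to 72 patients switch; the upper figure is half of 145, from the protocol's statement that about half of planned patients would be affected. The monotherapy rates in Section 2.3 then give 36 × 0.062 = 2.2 to 72 × 0.062 = 4.5, and 36 × 0.171 = 6.2 to 72 × 0.171 = 12.3. The combination studies that the protocol cites would put the number near zero. This range is too wide, and its source too remote, to serve as an estimate.

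**The case against.** Several counter-arguments are sound and limit the point.

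- A reader might infer that Appendix F cannot act on 24 mg at all. The documents do not support that. Appendix F 1 prompts testing on symptoms, Section 8.2.1 allows extra samples if clinically indicated, early discontinuation triggers a full visit, and a data monitoring committee has access to treatment codes. None of these reliably finds an asymptomatic rise.
- A reader might infer that there is no pre-switch creatinine. There is one at Visit 9, and Appendix F uses the pre-randomisation creatinine as its reference in any case. The missing reference concerns only the other chemistry, haematology, dipstick and ECG.
- A reader might infer that 24 mg safety rests on one value. The follow-up visit 4 weeks after treatment repeats the laboratory tests and ECG, and Section 9.4.2.2 compares 24 mg with concurrent placebo at 12 months. Follow-up values are off drug, however, so they do not restore the chance to pause it.
- Monotherapy rates may not carry over, because verinurad is given here only with allopurinol. This stands, and it is why no patient count is claimed.
- Section 4.3 gives pharmacokinetic reassurance: the expected Cmax at 24 mg is below that seen in healthy subjects, and the AUC only slightly above. This speaks to the expected risk, not to whether the monitoring rules can operate.
- The 4-week titration spacing is justified by allopurinol skin reactions, and creatinine intervals after Week 20 are already 13 to 14 weeks. Both are true, but those later intervals were set for patients on an unchanged dose.
- The Visit 8 and Visit 9 eGFR sentences are separate conditions, not a contradiction. That is fair; what is missing is how the second relates to dispensing.

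**Conclusion.** The point holds in a limited form. Over a nominal 13 weeks on 24 mg (11 to 15 with windows), no scheduled creatinine precedes the visit at which treatment ends. The creatinine and eGFR rules depend on unscheduled testing, and an asymptomatic rise would normally be found only at Week 60. For the other chemistry, haematology, dipstick and ECG, the last pre-switch value is 13 weeks old, and a change from it to Week 60 mixes equal periods on 3 mg and 24 mg.

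This rests on the schedule alone and needs no assumption about event rates. How many patients would be affected is unknown, possibly none. The Week 34 primary analysis precedes the switch and is unaffected, so this is an inexpensive safety improvement that should be made, not a flaw that undermines the trial's main conclusion.

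**What to change.** 1. Add the Visit 8 safety laboratory panel and dipstick, and the ECG if feasible, to Visit 9 for all patients entering the new regimen. Blood is already drawn there. The safety summaries would then need to show change from Visit 9 as well as from baseline.
2. Reconcile the Week 47 to 60 schedule with Appendix F and with Section 2.3's reliance on monitoring, by scheduling a creatinine/eGFR sample while 24 mg can still be interrupted. Take it in every arm of the new regimen to keep the blind. The timing is for the sponsor to set.
3. Reconcile the Visit 8 eGFR gate, the Visit 9 sentence on eGFR below 30, and dispensing at the end of the visit. The clinical rule is the sponsor's; this review proposes none.

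**Cost.** Item 1 is extra tubes, a dipstick and possibly an ECG at an existing visit. Item 2 is one short blood draw per new-regimen patient. Item 3 is wording.
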